- Availability of space to have ocular fundus and OCT cameras on site, including the following to be installed and maintained by the Sponsor, only for the purposes of the study

- Availability of staff to train and take fundus photographs per IDx-DR imaging protocol
- Internet connection and computer hardware (supplied) for operation of the IDx-DR device and eCRF forms
- Willing to administer tropicamide 1.0% eye drops to participants that do not provide images suitable for IDx-DR analysis with undilated eyes
- Previous experience with clinical studies preferred or demonstrated aptitude for conducting study
- Willingness to allow a FPRC-certified ophthalmic photographer onsite for "Gold Standard" reference standard imaging using the Maestro system

2. NW400 Camera Operators at Sites

All personnel who will be taking fundus images and operating the IDx-DR device will be documented and trained as per the IDx training protocol to become NW400 operators. NW400 operators must attest to the

fact that they have not had previous experience operating a fundus imaging system prior to participating in this study. Training for the NW400 camera operators will consist of written materials and a standardized training session on the use of the IDx-DR Client, the image quality feedback mechanism, and operation of the NW400 fundus camera. Written materials include the fundus camera operator manual, a quick reference guide for operations, image quality, and troubleshooting, and training certification checklist. NW400 operators will self-certify as IDx-DR photographers by successfully submitting exams to IDx-DR. Following certification, these photographers will be referred to as qualified 'NW400 operators'.

D. Overview of Primary Care Enrollment & Data Collection Process

- Potential participants are first identified by the primary care physician or staff using patient history.
- Potential participants are further evaluated by a site research coordinator who determines eligibility using the inclusion and exclusion criteria.
- The research coordinator or Investigator discusses the trial and obtains informed consent. The participant is now in the participant population and is assigned an identification code for the study.

-	
-	
_	

E. Masking Protocol

IDx has chosen an independent data storage center for the clinical trial. The IDx-DR software will be locked prior to initiating the clinical trial. A copy will be placed in escrow prior to the start of enrollment for auditing purposes.

F.	Configurable Output Testing
G.	Primary Care Imaging Procedure
	1. IDx-DR SCREENING PROCEDURE (Topcon TRC-NW400 Imaging Platform, by the NW400 operator)
	ng and IDx-DR submission activities should follow the instructions included with the R device
וטג-ט	2. 4-W & OCT REFERENCE STANDARD IMAGING (by the FPRC certified photographer)

1.

X. STUDY DESIGN (ENRICHED COHORT)

A. Participant Inclusion criteria for enriched cohort:

- 1. Diagnosis of diabetes mellitus (as defined above in Section IX.A, except as follows): HbA1c and/or FPG level as defined by statistician during enrichment period
- 2. Age 22 or older
- 3. Understand the study and volunteer to sign the informed consent

B. Participant Exclusion criteria:

- Persistent vision loss, blurred vision, or floaters.
- Diagnosed with macular edema, severe non-proliferative retinopathy, proliferative retinopathy, radiation retinopathy, or retinal vein occlusion.
- History of laser treatment of the retina or injections into either eye, or any history of retinal surgery.
- Currently participating in another investigational eye study and actively receiving investigational product for DR or DME.
- Participant has a condition that, in the opinion of the investigator, would preclude participation in the study (e.g., unstable medical status including blood pressure or glycemic control, microphthalmia or previous enucleation).
- Participant is contraindicated for imaging by fundus imaging system used in the study:

- Participant is hypersensitive to light
- Participant recently underwent photodynamic therapy (PDT)
- Participant is taking medication that causes photosensitivity

[figure not shown]
C. Clinical Site Selection

[figure not shown]
All sites will participate in enrichment, if implemented, and will be willing to administer HbA1c or FPG tests on participants to determine eligibility for enrollment, if the participant's medical record lacks adequate documentation to establish the diagnosis of diabetes meeting an enrichment criteria, or for de novo patients being screened for study inclusion.

D. Primary Care Imaging Procedure

[figure not shown]

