Participants in the study will be assessed at the primary care site for the purpose of determining eligibility. This assessment includes a review of medical records and questions asked by primary care personnel or clinical study staff. Participants will be confirmed for a diagnosis of diabetes by testing or a review of medical history, and will be asked whether they have persistent vision loss, blurred vision, or floaters. They will also be asked if they are contraindicated for fundus photography on the Topcon NW400 on the basis of hypersensitivity to light, recent photodynamic therapy (PDT), or taking of medication that causes photosensitivity. These terms will be explained as part of the eligibility determination process and in the informed consent document. Participants will be asked whether they are diagnosed with macular edema, severe non-proliferative retinopathy, proliferative retinopathy, radiation retinopathy, or retinal vein occlusion. They will also be asked if they have any history of laser treatment of the retina or retinal surgery (including intraocular injections). The site may also review the participant's records for the same information. The initiation, continuation or discontinuation of medical therapy will remain at the discretion of the Investigator, as this is not expected to be dependent on any aspect of participation in this research study.

C. Reading Center Assessment and CRO Follow-Up

The Reading Center will be providing an EDTRS result for each participant in the study within 2-10 weeks of their completion of the study protocol.

To ensure patients are appropriately referred to an eye care professional based on Reading Center grades, all adjudicated ETDRS Reading Center results will be converted to an ICDR level by the CRO based on the American Academy of Ophthalmology's (AAO) International Clinical Diabetic Retinopathy (ICDR) Disease Severity Scale (http://www.icoph.org/downloads/Diabetic-Retinopathy-Detail.pdf). ICDR results provided to sites will also indicate whether the Reading Center detected macular edema (ME).

To support referral determinations based on ICDR results provided to them by the CRO, participating clinicians should review the Management Recommendations for Patients with Diabetes as contained in the AAO's Preferred Practice Pattern (AAO PPP) Recommendations for Diabetic Retinopathy (See Table 6 at http://www.aao.org/preferred-practice-pattern/diabetic-retinopathy-ppp-updated-2016).

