1. Methods and Timing for Assessing, Recording, and Analyzing Safety Parameters

Safety will be evaluated during the time the participant is in the study which will include from the time of consent through the time of exit which will typically be less than one day. Safety will be assessed by frequency and incidence of ADEs and UADEs.

Because this is considered a device study, it is consistent to use the following definitions when assessing safety issues:

- Adverse device effect (ADE), which means an adverse event related to the use of an investigational medical device.
- Unanticipated adverse device effect (UADE), which means any serious
 adverse effect on health or safety or any life-threatening problem or death
 caused by, or associated with its use that had not been previously identified
 in nature, severity, or degree of incidence.

2. Identification of Events and Timeframe for Reporting

For the purpose of this study, ADEs and UADEs will only be recorded for the duration of the participant's involvement in the study, which will be less than one day. Many participants in this study may have pre-existing medical conditions however, those pre-existing conditions will not be considered as ADE/UADEs, unless use of the study device elicits a new ADE/UADE or worsens an existing condition in terms of frequency or intensity during or immediately after the use of the study device. All reportable events as defined above, determined to be an ADE/UADE will be recorded in the source documents and entered in the electronic case report form (e-CRF). The investigator will provide the date of onset and resolution, intensity, frequency, action(s) taken, changes in study device application, relationship to study device, and outcome.

3. Follow-up of Adverse Device Effects

ADEs that occur on the day of the visit will be followed up to adequately evaluate the participant's safety or until the event stabilizes. When the event resolves, a resolution date should be documented on the case report form. All UADEs will be followed until resolution or until the participant is medically stable. All other events that cannot be resolved by 30 days after the last study contact will be considered resolved by convention and entered in the electronic data capture (EDC) system.

4. Guidelines for Assessing Intensity of an Adverse Device Effect

The investigator should use the following definitions when assessing intensity of an adverse event:

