#### 4.7.7.6. Handling of Withdrawals

Subjects may be withdrawn from the study by any of the following mechanisms:

1. Voluntary withdrawal of consent to participate by the subject at any time during the study.
2. Determination by the clinical investigator that it is in the best interest of the subject.
3. Determination by the sponsor or CRO it is in the best interest of the subject.
4. Subject ineligibility.
5. Inability for the subject to come in for 4-W photos.

All data available from enrollment to subject withdrawal will be collected unless the subject withdraws consent from the study. Data will be collected for subjects who discontinue participation but who do not withdraw consent.

[REDACTED]

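### Device effects that begin on a day after the visit fall outside the protocol's recording rule, which conflicts with its open-ended routes for serious events

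*Protocol*

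**What the plan says.** Protocol VII.D.1 sets the safety evaluation period as "from the time of consent through the time of exit which will typically be less than one day". It names the frequency and incidence of ADEs and UADEs as the safety measure.

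VII.D.2 then limits recording: "ADEs and UADEs will only be recorded for the duration of the participant's involvement in the study, which will be less than one day". It mentions time after device use only once, in saying when a pre-existing condition counts: if the device "worsens an existing condition in terms of frequency or intensity during or immediately after the use of the study device".

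VII.D.3 on follow-up says that "ADEs that occur on the day of the visit will be followed up to adequately evaluate the participant's safety or until the event stabilizes".

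VII.D.7 gives 7 days for entering recordable ADEs and 24 hours for recordable UADEs. Under VII.D.8, the automatic email to the medical monitor is generated when a UADE is entered in the safety database.

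Two other provisions set no time limit. The opening of VII.D has serious and unexpected events investigated at once by the CRO or sponsor. VII.D.9 has any possible UADE related to the device forwarded to the sponsor.

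**The concern.** The synopsis gives validating the device's safety as one purpose of the study, and the safety result is a count of ADEs and UADEs. The recording window therefore decides what that result can contain. VII.D.2 is worded as a restriction, not as a minimum: an effect beginning the next day is excluded even when the participant telephones the site to report it. Seriousness gives no exception, because the rule names UADEs, whose definition begins "Unanticipated adverse device effect (UADE), which means any serious".

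A second risk is inconsistency between sites. A site told of a possible UADE on a later day would be expected to forward it under VII.D.9, but under VII.D.2 it would have no rule for recording it. Sites could resolve this differently, and an event known to the sponsor could be absent from the reported incidence.

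**Working it through.** No arithmetic applies. The check sets the provisions side by side for three times of onset.

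| Onset | Recording (VII.D.2, with the period from VII.D.1) | Follow-up of ADEs (VII.D.3) | Entry deadlines and alert (VII.D.7, VII.D.8) | Forwarding and investigation (opening of VII.D, VII.D.9) |
|---|---|---|---|---|
| Before exit | Yes | Yes | Yes | Yes |
| Same day, after exit | No, read literally | Yes, read literally | Unclear | Yes, if serious and unexpected or a possible UADE |
| A later day | No | No | No | Yes, if serious and unexpected or a possible UADE |

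1. **Later-day onset.** VII.D.2 confines recording to the period of involvement, and VII.D.1 closes that period at exit. The deadlines in VII.D.7 apply to recordable events, and the alert in VII.D.8 depends on entry, so the exclusion carries through to both. The last column still applies, and that is the conflict.

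2. **Same-day onset after exit.** VII.D.3 speaks of the day of the visit, which is longer than the time to exit. The phrase in VII.D.2 about effects immediately after use qualifies pre-existing conditions and does not extend the window. The text does not settle this case.

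3. **Longer periods elsewhere.** VII.D.3 follows UADEs until resolution or medical stability and has a 30-day convention for unresolved events. VII.D.10 follows events until resolved or stable. All of these concern events already identified. None admits a new onset.

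4. **Length of participation.** VII.D.1 says *typically* under one day; VII.D.2 says it *will be* under one day. SAP 4.7.7.6 lists as a withdrawal reason "Inability for the subject to come in for 4-W photos", and Protocol VIII.C refers to inability to keep study visits. Both suggest that some participants may attend on more than one day. SAP 4.7.7.3 dates completion at the completed 4-W imaging. If that imaging fell on another day, the consent-to-exit period in VII.D.1 would already cover it, but the fixed duration in VII.D.2 would be wrong.

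**The case against.** The strongest reply is that serious events are already covered: the opening of VII.D and VII.D.9 route them onward without a time limit. This stands in part. A reader might infer from VII.D.2 that a late serious event could never reach the sponsor, or that monitors would have no ground to query one. The documents do not support either. The opening of VII.D also has monitors report unreported AEs or UADEs seen in study records, with no limit on onset. What remains is that none of these provisions says the event is recorded, and none lifts the word *only* in VII.D.2.

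The second reply is that a same-day window suits a minimal-risk imaging study. Protocol V describes minimal risk and minimal side effects of the dilating drops, and SAP 4.3 expects no formal safety events. An ADE must relate to the investigational device, which is software. The dilated reference imaging uses a separate cleared camera after the device result, so its dilation effects may not be ADEs at all. This stands as a limit on size. It does not explain why an effect that the site does judge device-related, and knows about, should go unrecorded.

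Two further inferences are unsupported:

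- Protocol VI.C returns Reading Center grades "within 2-10 weeks of their completion of the study protocol". A reader might take this as a risk period or a later safety contact. It describes grading turnaround and results sent to sites; no participant contact is scheduled there.
- Harm from acting on a device output is speculative. VI.C bases referral on Reading Center results, and much of the masking and workflow text is missing from the public version.

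A post-visit contact described in the missing text cannot be excluded, but it would still have to be squared with *only*.

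**Conclusion.** The point holds as a limited defect in safety recording that should be corrected. On the literal wording, a device effect beginning on a later day is not recorded and not counted, even when the site learns of it, while other sections require the serious ones to be passed on. Same-day onset after exit is unresolved, and the two statements of duration disagree.

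The size cannot be estimated. The documents give no distribution of onset times, so no share of events lost can be stated. Given the protocol's own rating of risk, the practical effect is probably small. Sensitivity and specificity are not touched.

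The conclusion assumes that *only* is meant literally, that involvement ends at exit as VII.D.1 says, and that nothing in the unavailable text provides for recording later events.

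**What to change.** Amend the protocol wording in three places:

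1. In VII.D.1 to VII.D.3, provide that any suspected ADE or UADE the site learns of after exit, by whatever route, is recorded and enters the existing 7-day or 24-hour path. This also settles same-day onset after exit.
2. Reconcile VII.D.2 with the opening of VII.D and with VII.D.9, so that every event forwarded to the CRO or sponsor as a possible UADE is also recorded.
3. Replace the fixed statement of under one day in VII.D.2 with wording that agrees with VII.D.1 and runs through completion of 4-W imaging.

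The cost is a wording amendment, with no added visit or mandatory call. The drawback is that capture after exit is passive and incomplete. The report should say so wherever ADE and UADE rates are given.

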The photography protocol, as described below, consists of two images of the ocular fundus (one optic disc centered, one fovea centered), obtained from both eyes of enrolled participants using the NW400. If the NW400 camera operator is unable to obtain adequate images without dilation, the participant will be asked to remove contact lenses if they are wearing contacts and undergo reimaging under dilation using tropicamide 1% eye drops, administered under the supervision of a physician. After generating an IDx-DR screening result, a separate professional ophthalmic photographer certified by the Wisconsin Fundus Photography Reading Center (FPRC) will use a different, FDA-cleared camera system called the Topcon 3D OCT-1 Maestro (Maestro) to perform dilated W-4 four-field fundus photography, macular ocular coherence tomography (OCT) imaging, and imaging for the grading of media opacity. W-4 and OCT images using the Maestro will be sent to FPRC for primary and secondary reference standard evaluation.

The FPRC will determine the severity of retinopathy (including the presence of macular edema) according to the Early Treatment of Diabetic Retinopathy System (ETDRS) grading system based on the W-4 fundus photographs. OCT will also be used to assess the presence of diabetic macular edema (DME) according to FPRC grading protocols. Incidental findings will also be documented by the FPRC, including review of grading for media opacity.

In order to assure an adequate range of DR conditions in the study population for sensitivity and specificity analysis, the study population will be enriched with participants at higher risk for vtDR. The enrichment cohort will be targeted using HbA1c and/or FPG levels, if needed.

The performance of the IDx-DR device will be compared to the FPRC readings in terms of sensitivity and specificity, in addition to conducting stratification based on media opacities and participant demographics, including ethnicity and race, cataract, incidental findings, and referral attrition. Endpoints will be calculated according to the Statistical Analysis Plan (SAP).

IV. CRITERIA FOR EVALUATION

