- MILD: Participant is aware of symptoms or has minor findings but tolerates them well, and no or minimal intervention required
- MODERATE: Participant experiences enough symptoms or findings to require intervention
- SEVERE: Participant experiences symptoms or findings that require significant medical intervention

5. Guidelines for Determining Causality

The investigator will use the following question when assessing causality of an ADE/UADE to study device, where an affirmative answer designates the event as a suspected ADE: Is there a reasonable possibility that the device or its use caused the event? "Reasonable possibility" means that there is evidence to suggest a causal relationship between use of the device and the ADE.

6. Discontinuation Due to ADEs/UADEs

Participants may be withdrawn from the study at any time. Participants withdrawn from the study due to an ADE, whether serious or non-serious, must be followed by the investigator until the clinical outcome from the ADE is determined. Any participant who experiences an ADE may be withdrawn at any time from the study at the discretion of the investigator. The ADE(s) should be noted on the appropriate CRFs,

and the participant's progress should be followed until the ADE is resolved. The medical monitor or project manager must be notified.

7. Reporting Procedures

All recordable ADEs will be entered into the safety data system within 7 days of identification. Recordable UADEs will be entered into the data system within 24 hours of identification. If there are any technical difficulties, the UADE will be reported by telephone or fax communication. This data will be entered into the EDC as soon as the system is available.

8. Unanticipated Adverse Device Effects

Any UADE entered in the safety database by a site investigator will generate an automatic email notification to the sponsor IDx-DR Medical Monitor. The sponsor is obligated to investigate UADE reports promptly to determine reporting requirements of the event and assess if the event warrants further action by the sponsor.

9. Regulatory Reporting

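### Protocol VII.D requires recording only of events judged at least possibly device-related, so in the visible text a non-serious reaction to the dilated W-4 reference imaging need not be recorded or counted

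*Protocol*

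**What the plan says.** Protocol VII.D.1 sets the safety measure: "Safety will be assessed by frequency and incidence of ADEs and UADEs". It explains the scope with "Because this is considered a device study, it is consistent to use the following definitions when assessing safety issues" and defines an ADE as "an adverse event related to the use of an investigational medical device". A UADE must be serious.

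VII.D.2 gives the recording rule: "All reportable events as defined above, determined to be an ADE/UADE will be recorded in the source documents", with entry in the e-CRF. VII.D.5 decides what qualifies by one question: "Is there a reasonable possibility that the device or its use caused the event". A yes makes the event a suspected ADE. VII.D.7 sets entry deadlines of 7 days for ADEs and 24 hours for UADEs, and none for any other event.

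Protocol III describes the reference imaging. "After generating an IDx-DR screening result, a separate professional ophthalmic photographer" uses a different cleared camera, the Maestro, "to perform dilated W-4 four-field fundus photography" together with OCT. SAP 3.6 states that all subjects are imaged on the 4-W protocol.

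Elsewhere the wording is broader. Protocol V and the opening of VII.D speak of AEs as well as UADEs: the CRO reviews AEs that sites submit, and monitors flag any that went unreported.

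**The concern.** The rule asks for a causality judgment first and a record second, and the only cause considered is the study device. That device is the IDx-DR software (title page and synopsis). The W-4 step is study-required, involves dilation, and takes place after the device has finished its work. An event there can fall outside every category that the protocol tells sites to record.

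Two things are at stake. The safety listing can be silent about a procedure that every participant undergoes only because of the study. And where an investigator decides that an event was not device-related, nothing need exist in the study records for a monitor to review. Sites may also apply the rule differently, because some sections say AE and others ADE.

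**Working it through.** There is no plan figure to reproduce, so the main check is to take one case through the rules. The case is a non-serious reaction to dilation or photography at W-4.

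1. **Is it an ADE (D.1)?** It would have to be related to use of the investigational device. W-4 comes after the IDx-DR result, with another photographer and another camera, and it supplies the reference standard. It is not use of IDx-DR, so no.
2. **Does D.5 bring it in?** The threshold is low, since a reasonable possibility is enough, but the question concerns only the device or its use. No.
3. **Is it a UADE (D.1)?** It is not serious. No.
4. **Must it be recorded (D.2)?** Only events determined to be an ADE or UADE must be. No.
5. **Must it be entered (D.7)?** The deadlines cover ADEs and UADEs only. No.
6. **Is it counted (D.1)?** Only ADEs and UADEs are. No.

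The provisions that might close the gap are these:

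- *Protocol V and the VII.D introduction* cover review of AEs that are submitted and flagging of unreported ones. Neither defines an AE or tells a site to record one unrelated to the device.
- *VII.A monitoring* includes adverse events and checks data against source, but D.2 requires a source entry only for ADEs and UADEs.
- *The relationship-to-device item in D.2* is completed for events already in the record.
- *D.3, D.4 and D.10* use looser terms (other events, adverse event), but they govern follow-up and intensity grading, not what is recorded.
- *The route for serious and unexpected events in VII.D* does not reach a non-serious reaction.
- *SAP 4.3* expects no formal safety events, and the visible SAP contains no safety analysis that would count other events.

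**What a zero count would mean.** The only input is n = 845, the planned number after exclusions (synopsis; SAP 2.1.1), taken here as the number who have W-4 imaging. Safety runs from consent, so the safety denominator is at least this. If every event were recorded and none occurred, the one-sided 97.5% upper bound would be

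1 − 0.025^(1/845) = 0.00436, or 0.44%.

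Under the present rule that calculation is not available for W-4, because a zero may mean either that no reaction occurred or that none had to be entered.

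**The case against.** The strongest reply is that the scope is a stated and reasoned choice. The protocol calls this a device study, runs it under abbreviated device requirements, and aims to assess the safety of the device. On that aim the ADE/UADE count is the right measure, and it can stay as planned.

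The mixed use of AE and ADE may also be loose drafting. Protocol V refers to the camera systems in the plural and to tropicamide, and then to review of reported AEs, so a site could reasonably take imaging and dilation reactions as covered. That is a fair reading of intent, but it does not supply a duty to record.

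Text is also missing from the public copy. VII.C, the workflow steps in IX.D, the imaging procedures in IX.G and SAP 5 are blank or blacked out and could hold instructions for reference imaging. The point therefore applies to the visible text only.

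A reader might infer several stronger things that the documents do not support:

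- *That observation stops too soon after W-4.* SAP 4.7.7.3 gives a completion date, not the length of stay, and the procedure text that would show it is removed.
- *That a known number of reactions would be missed.* No reaction rate, and no share of subjects dilated at the NW400 step, is given.
- *That reactions to drops given for NW400 re-imaging also escape.* Dilation is part of the device's image-capture workflow, and D.5 needs only a reasonable possibility, so these are most naturally suspected ADEs.
- *That the study fails to confirm its own minimal-risk statement.* Protocol V rests that statement on prior clearance, drug approval and a cited source, and does not promise that this study will test it.

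**Conclusion.** The point holds for the visible text. VII.D requires recording and counting only of events judged at least possibly related to use of the study device. A non-serious reaction to the dilated W-4 imaging falls outside that rule, and an event judged unrelated need leave no record to audit. Because this follows from a stated rule, it is more than a missing detail.

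The consequence is limited. The number of unrecorded events cannot be derived. What is lost is the ability to read a zero count as information about W-4, which with complete recording in 845 subjects would mean an upper bound of 0.44%. Sensitivity, specificity and the device ADE/UADE rate are untouched.

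The conclusion rests on two assumptions: that the study device means IDx-DR (named as the investigational product and again in VII.D.9), and that the removed sections contain no separate recording rule. It is a cheap improvement to the safety record. It is not a flaw in the device evaluation, and nothing in the documents suggests that reactions were deliberately excluded.

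**What to change.** - In VII.D.1 and D.2, record every adverse event from consent to exit before judging relatedness.
- In D.5, attribute each event to one of: (a) IDx-DR and its NW400 workflow, including dilation for NW400 re-imaging; (b) the W-4/OCT reference imaging, including its dilation; (c) neither or indeterminate. Each dilation then belongs to one step, and (c) takes events that cannot be assigned, for example in a subject dilated for both steps.
- Keep the device ADE/UADE frequency and incidence as the planned safety measure, and list the other events separately.
- Use the same AE and ADE terms in Protocol V and throughout VII.D.

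The cost is protocol wording and an attribution field on the existing e-CRF, with no new visit or procedure. The downside is a few more minor events to enter and a slightly less favourable overall event listing.

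### Protocol VII.D.3 records adverse device effects still open or of unknown status 30 days after last contact as resolved, and does not say how this fits the follow-up duties in D.6 and D.10

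*Protocol*

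**What the plan says.** Four parts of Protocol section VII.D bear on this point.

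- **D.2** makes outcome one of the items the investigator supplies for each recorded event, at the end of a list that closes with "changes in study device application, relationship to study device, and outcome".
- **D.3** has adverse device effects (ADEs) from the visit day followed far enough to evaluate safety "or until the event stabilizes". On dates it says: "When the event resolves, a resolution date should be documented on the case report form". It treats UADEs separately: "All UADEs will be followed until resolution or until the participant is medically stable". For the rest it sets the closing rule: "All other events that cannot be resolved by 30 days after the last study contact will be considered resolved by convention", with entry in the EDC.
- **D.6** says that a participant withdrawn because of an ADE, "whether serious or non-serious, must be followed by the investigator until the clinical outcome from the ADE is determined". It adds that progress should be tracked to resolution.
- **D.10** lets follow-up of ADEs and UADEs end once the event has resolved or is judged stable.

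D.1 gives the planned safety measure: "Safety will be assessed by frequency and incidence of ADEs and UADEs". The visible SAP text has no rule for the outcome or duration of adverse events.

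**The concern.** The rule is triggered when an event cannot be resolved by the cut-off, and the status it then assigns is 'resolved'. A data cut-off needs a date after which nothing more is collected. It does not need a status that contradicts, or goes beyond, what the site knows.

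Two things are at stake. The first is the accuracy of the safety record in a study that SAP 2.1.1 describes as pivotal and for registration. An event that lasted more than a month would appear in the outcome field like one that cleared up. The second is follow-up. D.6 and D.10 both use resolution as an endpoint for following the participant, so a deemed resolution in D.3 could be taken to meet it.

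**Working it through.** No arithmetic applies, because the point concerns a recording rule and its fit with neighbouring sections. The check was to compare the sections.

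1. **Scope.** D.3 exempts only UADEs. Under D.1 a UADE must be a serious effect, a life-threatening problem or a death, and must not have been identified before. The closing rule therefore reaches non-serious ADEs and also any serious ADE of a kind already identified.

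2. **Status at the cut-off.** An event that D.3 closes can be in one of three states:

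| True status at 30 days | D.3 entry | Is the entry accurate? | D.10 follow-up | D.6 follow-up, if withdrawn for the ADE |
|---|---|---|---|---|
| Open, not stable | Resolved | Wrong | Continues | Continues |
| Open, but stable | Resolved | Wrong: the true label is 'stable' | May end | Continues until the outcome is determined; should track to resolution |
| Unknown, no further information | Resolved | Unverified | Endpoint not shown to be met | Endpoint not shown to be met |

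In no row is the entry supported by what the site knows.

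3. **Fit with D.2.** D.2 asks the investigator for the outcome. In all three rows D.3 puts a convention in its place.

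4. **Fit with D.10.** D.10 names resolution and stability as separate endpoints, and D.3 itself lets UADE follow-up end at medical stability. The protocol already has a truthful label for the second row and does not use it for non-UADEs.

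5. **Fit with D.6 and D.10 on duration.** Neither section has a day limit or mentions D.3, and D.3 mentions neither. Nothing in D.3 tells a site to stop following anyone. The gap is a missing statement of which text governs once an event has been deemed resolved.

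6. **Effect on planned results.** Frequency and incidence count whether events occur. Changing an event's outcome from open to resolved neither adds nor removes an event, so both measures change by zero. Sensitivity and specificity do not use adverse event data.

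7. **Number of events.** This cannot be derived. The documents give no ADE rate and no share of events lasting beyond 30 days. SAP 4.3 expects no formal safety events, Protocol V describes the risk as minimal, and D.2 limits recording to participation of less than a day. All of this points to few events or none.

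**The case against.** The strongest defence is that D.3 is an openly labelled closing convention. The words 'by convention' mark the status as administrative, so the protocol does not claim clinical resolution. D.3 governs what is entered; D.6 and D.10 govern how long participants are followed. 'Last study contact' is undefined, and if the telephone follow-up allowed by D.10 counts as a study contact, the 30 days begin only when follow-up is over and no conflict arises. The true status may also be recoverable: D.3 ties the resolution date to actual resolution, events are in source documents, VII.A has monitors check data against source, and VII.B keeps serious event summaries at the site.

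Much of this stands, and it limits the point:

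- A reader might infer that every entry made under the rule is false. The text does not support that. 'Cannot be resolved' can cover events the site is unable to close for lack of information, and for those the entry is unverified, not shown to be false.
- A reader might infer that D.3 ends follow-up at 30 days. It contains no such instruction, and its own first sentence sets no day limit.
- A reader might infer that serious events will be misreported. The rule could reach a serious ADE already identified, but the documents name none, so that case is hypothetical.

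The defence does not remove the fault. The protocol nowhere says that D.3 is only a database rule, and a definition of 'last study contact' that would remove the conflict is not given. A site that enters 'resolved' is complying with D.3, so a monitor need not query it. An EDC flag for such entries may exist, but neither the text of VII.C nor the eCRF codes are available, so this cannot be checked.

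**Conclusion.** The point holds as a minor fault in the safety record. Following D.3 as written puts a wrong outcome (event still open) or an unverified one (status unknown) in the EDC for non-UADE events not resolved by the cut-off, and it loses the distinction between stable and resolved. The relation to D.6 and D.10 is an ambiguity that could shorten follow-up at a site that reads the convention literally; it is not a stated rule.

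This conclusion rests on the wording of D.2, D.3, D.6 and D.10 and needs no assumed event rate. The number of events affected is unknown and probably very small. If no ADE is open at 30 days, the rule has no effect. ADE frequency and incidence, sensitivity, specificity, Type I error and sample size are unchanged in any case. Confidence is high on the wording and lower on the recorded data, because the EDC design cannot be seen.

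**What to change.** Keep the 30-day cut-off for data collection and change what is recorded at it. In D.3:

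- Replace the deemed resolution with the actual status at last contact: 'not resolved/ongoing', 'stable' or 'unknown'.
- Leave the resolution date blank for these events.
- List them in the safety report.
- State that the cut-off closes data entry only and does not end the follow-up required by D.6 and D.10.
- Define 'last study contact', saying whether follow-up calls count.

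The cost is a short protocol edit and, if the eCRF lacks these choices, an added outcome code. Sample size, endpoints and timeline are not affected.
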